### 2.a Gastrointestinal function and iron deficiency anaemia

The relationship between IDA and gastrointestinal functions including gastric acid secretion has been studied in children and adults. Nieman and his colleagues studied 14 iron-deficient infants and children, and observed profound suppression of gastric acid secretion in majority of the subjects (Niemann et al 1964). Studies in India have observed reduced gastric acid secretion in children (Ghosh et al 1972) and in adults (Sherman et al 1966) with iron deficiency anaemia. Reduction of acid secretion including histamine-fast achlorhydria also been reported in other Indian studies (Desai et al 1967, Desai et al 1968); compared to controls, acid outputs were significantly reduced in patients with iron deficiency. Histological abnormalities of the gastric mucosa suggestive of chronic gastritis were demonstrated in 61% of the patients in these studies. Other studies have observed very high incidence (75%) of chronic gastritis with iron deficiency anaemia (Ikkala & Siuarala 1964). However, it is not known if these abnormalities precede iron deficiency anemia. An early acquisition of infection in children in developing countries suggests that Hp-related chronic gastritis might precede iron deficiency anaemia in these countries.

### 2.b Etiology of IDA

In the developing countries, IDA may result from several, overlapping etiologies, however, low Fe bioavailability plays a major role (Taylor et al. 1995). Diets in many developing countries are cereal-based, and thus high in phytic acid, a potent inhibitor of Fe absorption (Hallberg et al. 1987, Hurrell et al. 1992, Davidsson et al. 1994a). They are also low in major Fe absorption promoters such as ascorbic acid (Layrisse et al. 1968, 1984, Martinez-Torres et al. 1970, Taylor et al. 1986, Hallberg et al. 1986, 1989, Siegenberg et al. 1991, Davidsson et al. 1994a). The overall Fe bioavailability from such diets can be expected to be low or very low, resulting in reduced absorption of Fe while the requirements are relatively high in infants, children and women of childbearing age. High prevalence of infectious diseases, and other nutritional deficiencies in

Principal Investigator (Last, first, middle): [name]

developing countries can also contribute to the development of IDA; gastrointestinal parasites such as hookworm (Stoltzfus 1997a), malaria (Stoltzfus 1997b), and vitamin A deficiency (West 1996) are factors important in the etiology of anemia.

Hp infection is considered a factor for anemia and IDA- Hp infection, common in such condition, has been discussed in the etiology of anemia and IDA (Dufour et al. 1993, Rosenstock et al. 1996, Marignani et al. 1997, Yip et al. 1997). This gastrointestinal pathogen has a worldwide distribution, however, it is more prevalent in the developing countries. The frequency of Hp infection is high in India, where >80% become infected by 20 years of age (Graham et al. 1991); in Bangladesh, where its prevalence in adults and children has been reported to be as high as 85% ([name] et al. 1995). Once infected, Hp infection is believed to remain throughout the life causing chronic gastritis, which is a risk factor for development of gastric atrophy and gastric cancer (Kuipers et al. 1995). Gastric acid is considered to be one of the most important luminal factors necessary for optimal absorption non-haeme Fe (reviewed by Skikne et al. 1981). It is possible that Hp infections may reduce absorption of Fe by causing gastric atrophy and achlorhydria, or by causing transient hypochlorhydria during the active infections. Both of these mechanisms would result in an increased susceptibility to IDA. Furthermore, increased fecal blood loss in Hp-infected individuals may contribute to IDA (Yip et al. 1997).

### **3. Importance of *H. pylori* infection in IDA and Food fortification program to combat Fe deficiency**

Fe fortification of food is believed to be the most cost-effective approach to reduce Fe deficiency (Hurrell 1997, 1998). While Fe fortification programs have been relatively successful in industrialized countries, they had limited success in the developing countries (Hurrell 1997). This perhaps reflects differences in the aetiology of IDA in the developed versus the developing countries. If IDA is related to a lower bioavailability of Fe from diets such as cereals and legumes, fortification of such diets may not be the ideal method for Fe supplementation, unless it is protected from the inhibitors of absorption such as phytate. Ascorbic acid (Davidsson et al. 1994a, 1997, 1998) or Na2EDTA (INACG 1993) could be suitable for this purpose. If IDA is partly due to increased blood loss from gastrointestinal parasites, then their treatment will be required for the food fortification program to be maximally effective. Similarly, treatment of malaria and Hp-infection could be important. Treatment of these infections in the developing countries would be very expensive and impractical due to higher incidences of treatment failure/reinfection. Thus, addressing these issues is critical for implementation of a successful Fe-fortification program in such countries.

#### **3.1 Fe fortification**

Fe is the most difficult mineral to add to the foods. When added as water-soluble, highly absorbable forms such as ferrous sulfate, the soluble Fe rapidly causes unacceptable color reactions in the presence of many fruits and vegetables, and in stored cereal flours it rapidly catalyzes fat oxidation reactions leading to rancid products (Hurrell 1997). Food manufacturers are often obliged to use water-insoluble Fe compounds to fortify foods, especially in fortifying cereal flours and salt- food vehicles considered most useful for Fe fortification programs in the developing countries. These water-insoluble compounds cause no organoleptic problems, however, their absorption is largely dependent on the extent of their dissolution in the gastric juice.

Fortification compounds such as elemental Fe or ferric pyrophosphate, widely used to fortify cereal flours and weaning cereals, do not completely dissolve in the gastric juice of healthy subjects with normal gastric acid output, and also far less absorbed than ferrous sulfate (Hurrell 1997). On the other hand, ferrous fumarate is almost insoluble in water, however, it is readily dissolved in the gastric juice of healthy subjects, and its absorption in adults has been observed to be equivalent to ferrous sulfate (Hurrell et al. 1989). Ferrous fumarate is an interesting Fe fortificant, which has been used to fortify maize flour in Venezuela (Layrisse et al. 1996), has been proposed as a fortificant of chocolate drink powder (Hurrell et al. 1991), and has recently been selected for a pilot salt fortification programme organized by the Micronutrient Initiative in Bangladesh, Ghana and Guatemala (Micronutrient Initiative 1997, personal communication). However, there is a concern that a proportion of the population in the developing countries such as Bangladesh, are likely to have hypochlorhydria or achlorhydria due to Hp-infection and thus they may not be able to absorb Fe from ferrous fumarate fortified foods.

#### 4. Study objectives

Once acquired, Hp infection remains throughout the life, causing chronic gastritis, a risk factor for development of gastric atrophy and gastric cancer (Kuipers et al 1995). Gastric acid is the most important luminal factor necessary for optimal absorption of non-heme iron Fe (Skikne et al 1981). It is possible that Hp infection may reduce absorption of Fe consequent to gastric atrophy and achlorhydria, or due to a transient hypochlorhydria during active infections. Either of these mechanisms would result in an increased susceptibility of IDA. Hp-infected individuals have been found to have reduced levels of serum ferritin (Milman et al. 1998).

There is no published information on the relationship between Hp infection and gastric acid secretion. We plan to obtain information on the prevalence of reduced gastric acid secretion among Hp-infected subjects, and also hope to evaluate if Hp infection *per se* is a factor in causing IDA.

If, as hypothesized, Hp-linked hypochlorhydria is found to be a factor for IDA, it will help address an important issue with regards to effectiveness of Fe-fortification program since ferrous fumarate, that requires gastric acid for its bioavailability, is the used as Fe-fortificant in the developing countries.

#### 5. Significance

Results from the study will provide new information on prevalence of *H. pylori* infection, and its association with low gastric acid secretion as well as IDA. Thus, results of this study are expected to have important implications for the treatment and prevention of IDA in population of developing countries.

## Research Design and Methods

---

Describe in detail the methods and procedures that will be used to accomplish the objectives and specific aims of the project. Discuss the alternative methods that are available and justify the use of the method proposed in the study. Justify the scientific validity of the methodological approach (biomedical, social, or environmental) as an investigation tool to achieve the specific aims. Discuss the limitations and difficulties of the proposed procedures and sufficiently justify the use of them. Discuss the ethical issues related to biomedical and social research for employing special procedures, such as invasive procedures in sick children, use of isotopes or any other hazardous materials, or social questionnaires relating to individual privacy. Point out safety procedures to be observed for protection of individuals during any situations or materials that may be injurious to human health. The methodology section should be sufficiently descriptive to allow the reviewers to make valid and unambiguous assessment of the project. **(DO NOT EXCEED TEN PAGES, USE CONTINUATION SHEETS).**

---

This study has two parts to address its two objectives, which complement each other, and will be done, in sequence to test our hypothesis.

1. **First part:** To determine prevalence of *H. pylori* infection, low gastric acid secretion and IDA in Bangladeshi women in the reproductive age living in a peri-urban community of Dhaka City.
2. **Second part:** To conduct a randomized, double-blind, placebo-controlled field trial in the same population to determine if *H. pylori* infection is causally linked to iron deficiency anemia in this population.

### 1. Part 1: First Objective of the Study

**To determine the prevalence of *H. pylori* infection, low gastric acid secretion, and iron deficiency anaemia in Bangladeshi women in the reproductive age living in a peri-urban slum of Dhaka city.**

One hundred sixty (160) adult women aged, 20-40 years, living in Nandipara, a peri-urban community of Dhaka city will be screened for *H. pylori* infection using the  $^{13}\text{C}$ -urea breath test. Their gastric acid secretion will be assessed by the non-invasive, Electrical Impedance Tomography ([name] et al. 1997); and their body iron status will be determined. All subjects will be fully informed about the aims of the study and the procedures to be followed, and written informed consent will be obtained before their enrollment in the study.

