### Specific Aims:

Describe the specific aims of the proposed study. State the specific parameters, biological functions/ rates/ processes that will be assessed by specific methods (TYPE WITHIN LIMITS).

The two specific aims of this study are:

1. to determine the prevalence of hypochlorhydria and iron deficiency anemia in *H. pylori*-infected women in the reproductive age, in a peri-urban slum of Dhaka city, and
2. to determine the if *H. pylori* infection is causally linked to iron deficiency anemia in this population.

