### 1.1.5 Sample Size

#### *Prevalence of HP-linked IDA and Hypochlorhydria*

The reported prevalence rate of *Helicobacter pylori* infection in the community is 80%. We assume 60% of the Hp-infected women will have hypochlorhydria and 70% of the Hp-infected hypochlorhydric women will have iron deficiency anaemia. However, we like to have an estimate of the prevalence of Hp infection plus hypochlorhydria plus iron deficiency anaemia to be corrected within  $\pm 5.0\%$  with 95% confidence

The required sample size will be:

$$\frac{\epsilon}{\sqrt{PQ/n}} = Z_{\alpha}$$

Where  $\epsilon$  = allowable error  
P = estimated prevalence  
Q = 1-P  
n = the required sample size  
 $Z_{\alpha}$  = value of the normal variation for (1- $\alpha$ )% confidence

Assuming:

$$\epsilon = 7.5\%$$

$$P = 0.8 * 0.6 * 0.7 \\ \cong 34\%$$

$$Q = 1-P = 66\%$$

$$\text{and } Z_{\alpha} = 1.96 \text{ (95\% confidence)}$$

The required sample size of Hp infected women with hypochlorhydria and IDA:

$$\frac{\epsilon}{\sqrt{PQ/n}} = Z_{\alpha}$$

$$\frac{0.075}{\sqrt{0.34 * 0.66/n}} = 1.96$$

Therefore  $n = 1.96^2 * 0.34 * 0.66 / 0.075^2$   
= 154 women. However, we will take 160 sample.

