## Facilities Available

---

Describe the availability of physical facilities at the place where the study will be carried out. For clinical and laboratory-based studies, indicate the provision of hospital and other types of patient's care facilities and adequate laboratory support. Point out the laboratory facilities and major equipment that will be required for the study. For field studies, describe the field area including its size, population, and means of communications. (TYPE WITHIN THE PROVIDED SPACE).

---

The study will be carried out under the Clinical Science Division of ICDDR,B. The study population will be recruited from Nandipara, a peri-urban community, situated 7 miles northeast of Dhaka city Centre. The community has a population of 4,500 with about 750 reproductive age women, in an area of approximately 3 square miles. The prevalence of Hp infection in women of this community is about 80%. Since 1985, ICDDR,B operates a weekly clinic for provision of care to the population for their minor illnesses.

Blood analysis including Hb, SF and sTfR, and measurement of gastric acid concentration will be performed in the laboratories of the Laboratory Sciences Division of ICDDR, B. Breath samples for UBT will be sent to the University of Basel, Switzerland where C will be measured by mass spectrometry (IRMS).

Principal Investigator (Last, first, middle): [name]

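### Part 1 of the H. pylori protocol sizes a community prevalence survey as a simple random sample but describes no sampling frame or random draw for its 160 women

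*Protocol*

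**What the plan says.** The file holds two unrelated protocols; this point concerns only the H. pylori one. Its first specific aim is "to determine the prevalence of hypochlorhydria and iron deficiency anemia in *H. pylori*-infected women in the reproductive age, in a peri-urban slum of Dhaka city".

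The women who enter Part 1 are described once, in section 1: "One hundred sixty (160) adult women aged, 20-40 years, living in Nandipara, a peri-urban community of Dhaka city will be screened". Facilities Available adds the place, "The study population will be recruited from Nandipara, a peri-urban community, situated 7 miles northeast of Dhaka city Centre", and the size of the source, "The community has a population of 4,500 with about 750 reproductive age women".

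Section 1.1.5 sets the precision target: "we like to have an estimate of the prevalence of Hp infection plus hypochlorhydria plus iron deficiency anaemia" with 95% confidence. It solves the ordinary one-proportion formula and arrives at 154 women, taken as 160. The margin appears as 5.0% in the sentence and as 7.5% in the calculation.

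In this protocol, chance selection is mentioned only for the allocation in Part 2 (sections 2.1 and 2.2) and for the occasions of the two tests in the validation of the acid-measurement device (section 1.1.3). Neither concerns which women of Nandipara enter Part 1.

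**The concern.** A margin of error from the formula in section 1.1.5 describes chance variation when every woman in the population has the same known probability of being drawn. If the 160 are found in some other way, the interval can still be computed, but it says nothing about how far those women differ from the rest of the community. How participants are chosen is settled at recruitment, so a protocol has to fix it; it cannot be left to an analysis plan.

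Selective entry is conceivable here. Each woman undergoes a breath test, a two-hour acid measurement with an injection, and a venous blood sample, and the ethics section offers diagnosis and treatment as the benefit. Women who feel unwell may be more willing, or less. Aim 1 is one of only two aims, and this estimate is what it delivers.

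There is also a smaller gap in wording. The aim speaks of reproductive age, the sample is limited to 20-40 years, and the protocol neither defines the first nor explains the second.

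**Working it through.** **Inputs.** From section 1.1.5: Z = 1.96; P = 0.8 × 0.6 × 0.7 = 0.336, rounded there to 0.34; margin 0.075 in the calculation; planned n = 160. From Facilities Available: about 750 women of reproductive age.

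**1. The plan's own figure.** n = Z² P(1 − P)/e² = 1.96² × 0.34 × 0.66/0.075² = 153.25, rounded up to 154. This reproduces. The formula has no design-effect or finite-population term, so it assumes a simple random sample.

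**2. Margin at n = 160.** 1.96 × √(0.336 × 0.664/160) = 0.073, or 7.3 points. P = 0.34 also gives 7.3. So the 7.5-point margin is met if the draw is random. The 5-point margin in the text is not met even then: it would need 1.96² × 0.34 × 0.66/0.05² = 344.8, that is 345 women, or about 237 with a finite-population correction for 750.

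**3. What selective entry would do (assumed values).** Let r be the probability that a woman with the joint condition takes part, divided by that of a woman without it. The survey then expects rP/(rP + 1 − P). With P = 0.336:

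| r (assumed) | Expected reading | Bias, points |
|---|---|---|
| 0.67 | 25.3% | −8.3 |
| 0.8 | 28.8% | −4.8 |
| 1.0 | 33.6% | 0 |
| 1.25 | 38.7% | +5.1 |
| 1.5 | 43.2% | +9.6 |
| 2 | 50.3% | +16.7 |

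The upward bias equals the half-width when the reading is 0.336 + 0.073 = 0.409. That gives r = (0.409/0.591)/(0.336/0.664) = 1.37. Downward, the same step with 0.263 gives r = 0.70.

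**4. A smaller bias also matters.** With standard error √(0.34 × 0.66/160) = 0.0374, the chance of an error above 7.5 points is 4.5% with no bias. It becomes 12%, 25% and 50% with an assumed bias of 3, 5 and 7.5 points.

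The documents give no value for r or for the bias. Steps 3 and 4 show sensitivity and do not predict a result.

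**The case against.** The strongest reply is that the protocol is silent, and silence is not a plan to take volunteers. It says the women live in and are recruited from Nandipara, calls Part 2 a field and community trial, and budgets four health workers. A proper draw may have been intended. That stands: the fault is that no method is described, not that a non-random one was chosen.

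Four stronger readings are tempting, and the documents support none of them.

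- A reader might infer that the women come from the institute's clinic, because Facilities Available notes that "ICDDR,B operates a weekly clinic for provision of care to the population for their minor illnesses". That sentence describes care; nowhere is the clinic named as a source of participants.
- A reader might infer that the estimate misses the population in the aim. The place matches, and women aged 20-40 are of reproductive age. Since that term is undefined, 20-40 could be its working meaning. Only the scope of the claim needs wording.
- A reader might infer that the Part 2 screening number depends on the Part 1 result. Section 2.3 computes 298 from the assumed 80%, 60% and 70%, before any woman is screened.
- A reader might take the biases in the table as the gain from random ordering. Working down a random list and replacing refusers leaves the same r among those approached. Random order removes selection by whoever does the recruiting, but not refusal bias.

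It is also fair that imbalance in a measured factor such as age could be reweighted later. That, however, requires a listed population with known ages, which the plan does not provide.

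**Conclusion.** The point holds in a limited form. Section 1.1.5 relies on a simple random sample that no section of the protocol provides for, so as written the 95% interval has no basis as a community estimate. Error from selective entry would lie outside the margin. Its size and direction cannot be derived from the documents. On the assumed model, a participation ratio of about 1.4 or more, or about 0.7 or less, would produce a bias larger than the 7.3-point half-width.

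The age restriction is a matter of stating what the estimate covers.

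The damage is confined to Aim 1. The Part 2 allocation is randomised among enrolled women, so its treatment comparison is not biased by this, and the 298 figure stands on its own assumed rates.

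**What to change.** In sections 1 and 1.1.5, state that the eligible women of Nandipara will be listed (about 750 are of reproductive age; the number aged 20-40 is not given), put in one random order and approached in that order. The first 160 to take part form Part 1, and the same list continues for the Part 2 screening. Record how many were approached and how many refused, with age, and report the participation rate beside the prevalence, because random order does not remove bias from refusals.

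State Aim 1 and its conclusion as women aged 20-40 in Nandipara, or define reproductive age as that range. While section 1.1.5 is open, make its two margins agree.

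The cost is listing one community of about 3 square miles where the institute has run a clinic since 1985, plus a log of refusals. No women or tests are added: the protocol already plans to screen 298, and 298/750 is about 40% of the women of reproductive age. The downside is somewhat slower recruitment than taking women as they come forward.

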#### 1.1 Methods

##### 1.1.1 Screening of Women for *H. pylori* Infection

$^{13}\text{C}$ -urea breath test (UBT) will be used for screening women for presence of *H. pylori* infection.

##### $^{13}\text{C}$ -urea Breath Test

*H. pylori* produces an enzyme, urease, which breaks urea to ammonia and carbon dioxide and the later is exhaled in the breath. This forms the basis of the "Urea Breath Test (UBT). The  $^{13}\text{C}$ -urea breath test (UBT) is based on the enzymatic degradation of labeled ( $^{13}\text{C}$ ) urea to ammonia,

Principal Investigator (Last, first, middle): [name]

and labeled CO2 that is exhaled in breath and thus can be collected and analyzed. The UBT has a high specificity (97-100%) and sensitivity (95-97%), and is widely used as a non-invasive technique for diagnosing current *H. pylori* infection (Lerlang et al. 1998, Logan et al. 1991, Vandenplas et al. 1992, [name] et al. 1997). This simple, non-invasive test is currently regarded as the "Gold Standard" for detection of *H. pylori* infection (Lerlang et al. 1998).

Breath samples will be collected for determining the baseline CO2 enrichment by blowing through a pipe directly into Vacutainer tubes after 2 hours of fast. Participating women will be asked to drink a glass of whole milk (200 ml), and 10 minutes later 100-mg C-urea (99%, Tracer Technologies, Boston, MA) in 25 ml of water. Thirty minutes later breath samples will again be collected in duplicates. Breath thus collected will be analyzed for C enrichment at the Department of Medicine and Research, University of Basel, Switzerland by mass spectrometry. Samples with excess enrichment over baseline (C enrichment of >3.5%) will be regarded as indicative of *H. pylori* infection.

